8 OBJECTIVES AND ENDPOINTS

Table 1. Objectives and Endpoints

	Objective	Endpoint	Analysis
Primary	Confirm the safety of the selected dose of PVSRIPO when delivered intracerebrally by convection-enhanced delivery (CED) in children with recurrent Grade III or IV MG	Percentage of patients that experience unacceptable toxicity during the 14-day period post-PVSRIPO treatment. Proportion of patients who require low-dose bevacizumab or steroid treatment due to an inflammatory reaction secondary to an immune response to PVSRIPO treatment will be calculated.	See Section 15.4
Secondary	Estimate Overall Survival (OS) in children with recurrent WHO Grade III and IV malignant glioma treated with a single dose of PVSRIPO	Proportion of patients alive 2 years after PVSRIPO treatment	See Section 15.5

Exploratory	Describe changes visualized on imaging due to intratumoral inoculation of PVSRIPO	Description of imaging changes	See Section 15.6
Other Exploratory	Describe changes in tumor volume visualized on imaging after intratumoral inoculation of PVSRIPO	Change from baseline in tumor volume based on imaging	See Section 15.7
Other Exploratory	Assess immunologic responses in peripheral blood and in serum	Change from baseline in immune function	See Section 15.7
Other Exploratory	Identify genetic predictors of response or failure of response to treatment with PVSRIPO	Identification of genetic markers as predictors of response	See Section 15.7

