- Whole blood (up to 10 mL) for immunologic analysis and PV titer (At the discretion of the Investigator, this blood sample, at least 2 years post-study drug infusion, may be obtained.)
- Whole blood (up to 76.5 mL, but not to exceed 3 mL/kg in a 24 hour period or 7 mL/kg in an 8 week period) for immunologic analysis (At the discretion of the Investigator, this blood sample, at least 2 years post-study drug infusion, may be obtained.)

Patients may not be treated with any other modality (other than bevacizumab per the ‘special considerations’ in Section 9.1.6) unless progressive tumor is noted or they are otherwise removed from the study. Patients will be considered off study upon tumor progression or upon treatment of the tumor with another modality. When subjects are considered off study, this indicates that subjects will no longer be obligated to undergo study-related tests and procedures, but the data described below will still be collected from these subjects as feasible. Subjects will be followed for serious adverse events for 30 days after coming off study. Collection of the following additional data from off study subjects will be performed, if possible, but is not mandatory and will not be considered a deviation if the data cannot be obtained. Subjects’ medical records will be reviewed for the remainder of their life, in order to collect data on subsequent treatments, disease progression, tumor size/volume, and survival. Follow-up activity will be at the discretion of the treating physician.

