12.6.2 Follow-up Requirements for Early Withdrawal

Subjects should be seen in clinic or contacted at a minimum of every 3 months for 1 year.

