12.7.3 Radiographic Review

A CT will be obtained to confirm catheter placement prior to beginning the PVSRIPO infusion. A MRI of the brain without gadolinium enhancement will be obtained within 4 hours of

completing the PVSRIPO infusion to monitor distribution of the infusion. A MRI of the brain with gadolinium enhancement will be obtained at all subsequent visits.

Given that imaging following immunotherapy differs greatly from what is typically seen following chemoradiation treatment or treatment with anti-angiogenic compounds, evaluation of response using with Macdonald criteria or RANO criteria is not appropriate in this trial. Immunotherapy can trigger an inflammatory immune response that is observed on imaging. Distinguishing between the inflammatory immune response and progressive disease is difficult. Therefore, an exploratory objective of this study is to describe radiographic imaging post-PVSRIPO treatment. Another exploratory objective of this study is to describe changes in tumor volume based upon radiographic imaging. For that reason, subjects who have gone off study may continue to be followed for collection of MRI measurements. For the purpose of this objective, relative tumor volume is estimated from the MRI using the metric of multiplying the widest tumor diameter with the perpendicular height of the tumor in that same slice.

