15.4.1 Overview of Study Design and Monitoring

Patients will be treated with PVSRIPO, then carefully monitored for safety for at least 1 year after treatment. Of particular interest will be the incidence of AEs that occur during the first 14 days after PVSRIPO treatment and the inflammatory events that occur during the first year after PVSRIPO treatment. The experience with PVSRIPO treatment of adult patients with recurrent WHO grade IV malignant glioma suggests that a patient remains at risk, during the first 12 months post-PVSRIPO treatment, of demonstrating neurologic or radiographic signs suggestive of an inflammatory reaction secondary to the immune response triggered by PVSRIPO that requires a dose of dexamethasone above 4 mg a day. As described in Section 9.1.6, such patients will be treated with bevacizumab 7.5 mg/kg IV every 3 weeks if possible, or alternatively corticosteroids or surgery.

Two sets of safety monitoring guidelines are proposed, with one focused on acute toxicity (i.e. occurring during the first 14 days after PVSRIPO administration), and one focused on long-term issues.

Acute Toxicity Monitoring Guidelines: Monitoring rules based upon the occurrence of an unacceptable toxicity, as defined in Section 9.1.5, during the first 14 days after PVSRIPO administration are shown below in **Table 4**.

If the number of patients with an unacceptable toxicity surpasses the noted thresholds, accrual will be suspended. Data will be carefully reviewed to determine if accrual should be terminated, continued without modification, or continued with appropriate modification (e.g. PVSRIPO dose reduction).

Table 4. Acute Toxicity Monitoring Rules.

# of Patients Accrued	Accrual Suspension Threshold
0 – 6	≥2 patients with unacceptable toxicity
7-9	≥3 patients with unacceptable toxicity
10-12	≥4 patients with unacceptable toxicity

The probability of study suspension and the expected number of treated patients before study suspension is tabulated below in **Table 5** as a function of the true underlying probability of an unacceptable toxicity.

Table 5. Probability of study suspension.

True Underlying Probability of a Unacceptable Toxicity within 14 days of PVSRIPO administration	Probability of Accrual Suspension	Expected Number of Patients to be Accrued
0.05	0.030	11.8
0.10	0.124	11.1
0.15	0.262	10.2
0.20	0.411	9.2
0.25	0.560	8.1
0.30	0.681	7.2
0.35	0.792	6.2
0.40	0.873	5.4

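### Mandatory follow-up ends at progression, so the inflammation endpoint and the 18-week rule can rest on optional data

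*Combined protocol and SAP*

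**What the plan says.** **What is promised.** Section 15.4.1 says patients will be treated, "then carefully monitored for safety for at least 1 year after treatment"; section 5.5 says much the same. Both name first-year inflammatory events as of particular interest, because adults stayed at risk for 12 months. The primary row of Table 1 and section 15.4.2 include the proportion of patients needing low-dose bevacizumab or steroids for a reaction to the study agent, and neither gives a time window. Section 15.4.2 adds a Kaplan-Meier summary of time to starting that treatment. Section 15.4.1 also interrupts enrollment if a single patient's reaction has not improved within 18 weeks of starting bevacizumab or steroids.

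**What is required.** Section 12.4 states: "Patients will be considered off study upon tumor progression or upon treatment of the tumor with another modality". Study tests then cease to be obligatory. "Subjects will be followed for serious adverse events for 30 days after coming off study". Further collection is to be done "if possible, but is not mandatory and will not be considered a deviation if the data cannot be obtained". It consists of lifelong record review for later treatments, progression, tumor size and survival. Section 13.1 requires adverse events to be recorded only up to the last study-related procedure. After week 48 follow-up is left to the treating physician, even for patients still on study.

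**Related text.** Section 12.7.3 sets aside the Macdonald and RANO criteria and says "Distinguishing between the inflammatory immune response and progressive disease is difficult". Section 12.6.1 lists disease progression as a possible reason for withdrawal by the investigator, and for early withdrawals section 12.6.2 says: "Subjects should be seen in clinic or contacted at a minimum of every 3 months for 1 year". The secondary endpoint in Table 1 is "Proportion of patients alive 2 years after PVSRIPO treatment".

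**The concern.** The plan wants to know how often children need treatment for inflammation over the first year, but the obligation to collect that information can end well inside the year. It ends at an event the protocol says is easily confused with the outcome. A reaction read as progression could stop the follow-up meant to record it, and the items collected afterwards would not show the error.

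Two things are at stake. One is a measure listed under the primary objective. The other is a one-patient safety trigger that protects children enrolled later, in a study that no longer spaces its patients 14 days apart (section 5.5). A reaction that is not improving is plausibly one at risk of being called progression.

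**Working it through.** **1. The plan's own figures.** Table 5 is the only computed operating characteristic. An exact sequential binomial calculation that checks Table 4 after each of up to 12 patients agrees with all eight suspension probabilities to within 0.005, and with expected accrual to within 0.1. At a true rate of 0.20 it gives 0.408 and 9.19, against 0.411 and 9.2 in the table. Table 5 covers only toxicity within 14 days, which the off-study rule barely touches.

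**2. The 18-week rule.** Inputs: 18 weeks (15.4.1) and 30 days (12.4).
- The rule needs 18 × 7 = 126 days from the start of inflammation treatment.
- If a patient goes off study *d* days after that start, required follow-up ends at day *d* + 30. The shortfall is 126 − 30 − *d* = 96 − *d* days.
- With *d* = 0 the shortfall is 96 days. It disappears only if *d* is at least 96.
- The 30 days cover serious events only. Failure to improve need not be reported as one.
- A reaction first treated at 12 months needs its outcome to about week 52 + 18 = 70. The last scheduled visit is week 48.

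**3. The year.** For a patient on the standard schedule who never progresses, the last visit is day 336, which is 365 − 336 = 29 days short.

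**4. The estimators.** Section 15.1 keeps all treated patients in every analysis, so the crude proportion counts a patient not observed after exit as having no reaction. Kaplan-Meier handles early exit only when exit is unrelated to the outcome, and the wording on progression casts doubt on that. Section 15.4.2 gives no rule for exit or for death. Censoring deaths would push the estimate of treated inflammation up, whereas unrecorded reactions push the crude proportion down.

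**5. Illustration for the crude proportion only.** The documents give neither times to exit nor reaction rates, so every input here is assumed. Let the reaction hazard be *h* = −ln(1 − *r*)/12 for a 12-month risk *r*, and the exit hazard *l* = ln 2/*m* for a median of *m* months. Exit is taken as independent of the reaction, deaths are ignored, and the 30-day tail (taken as one month) is assumed to catch every reaction. The recorded proportion is

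(1 − e^(−*h*)) + e^(−*h*) × *h*/(*h* + *l*) × (1 − e^(−11(*h* + *l*)))

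| True 12-month risk | *m* = 3 | *m* = 6 | *m* = 12 |
|---|---|---|---|
| 30% | 13% | 19% | 23% |
| 50% | 24% | 32% | 40% |
| 70% | 36% | 48% | 57% |

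Under these assumptions of independent exit, the planned Kaplan-Meier analysis would recover the true risk apart from small-sample noise. The table therefore does not measure bias from informative exit.

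**6. Survival.** With 12 patients, each unknown 24-month status widens the best-to-worst-case range by 1/12 = 8.3 points; three unknown give 3/12 = 25 points. If two were known alive and three unknown, the range would run from 2/12 = 16.7% to 5/12 = 41.7%.

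**The case against.** Several points on the other side have force.

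- *Survival.* A reader might infer that survival is cut off at progression. It is not: section 12.4 plans lifelong record review that includes survival, and section 15.5 counts time to last follow-up for those alive. What remains is that collection is optional off study and unscheduled after week 48.
- *Quarterly contact.* Section 12.6.2 may fill part of the gap, since progression is a listed withdrawal reason. Calling it a flat contradiction of 12.4 goes too far. But the plan does not say whether going off study counts as early withdrawal, when the year starts, or what the contact records.
- *Bevacizumab.* Section 12.4 exempts it when given for inflammation, so starting it does not itself end follow-up. Under 9.1.6 such patients return about every 9 weeks, so the second evaluation falls at 18 weeks. The 96-day gap therefore needs progression, or another tumor treatment, at about the same time.
- *Kaplan-Meier.* The planned analysis answers the simple complaint that a crude proportion ignores unequal follow-up. It does not answer the complaint about informative exit.
- *Confounding.* After progression and new therapy, attribution is blurred. Counting reactions only while on study would be a defensible descriptive choice, but the plan does not state it, and it sits badly with a promised year of monitoring.

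**Conclusion.** The point holds for inflammation and for the 18-week rule. Required ascertainment can stop well short of the promised year, for a reason that may be tied to the outcome, and the optional data do not name the items needed. The figures that rest on the documents alone are the 96 − *d* day shortfall, the 29-day gap at the end of the schedule, and 8.3 points for each unknown vital status.

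The size of the bias cannot be derived from the documents. A reader might infer a specific understatement of the inflammation rate, but any such number depends on assumed times to exit and applies to the crude proportion only. Even the direction is not settled, because progression could also be mistaken for inflammation.

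A reader might also call this a one-year co-primary endpoint. The plan lists it under the primary objective, sets no window and tests no hypothesis. The 14-day endpoint and the Table 4 rule are essentially unaffected. This should be fixed, but it does not undermine the acute-safety assessment.

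**What to change.** Reconcile sections 12.4, 12.6.2 and 15.4.1, and say whether going off study counts as early withdrawal. For every treated patient, regardless of progression or new therapy, require contact or record review every 3 months:

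- **To 12 months:** inflammatory reactions; steroids, bevacizumab or surgery given for them, with attribution; and the 18-week outcome. Continue until any open 18-week period has ended.
- **To 24 months:** vital status. Set the final survival cut-off at least 24 months after the last infusion and align section 12.5 with it.

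In Table 1 and section 15.4.2, define the inflammation endpoint over 12 months and state how death and progression are handled in its time-to-event analysis.

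The cost is amendment text and a short quarterly form for at most 12 patients. No treatment rule changes. The downside is that later events will be partly confounded by subsequent therapy, so attribution must be recorded and results read with that in mind.

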12.5 End of Study

The study will be considered complete once enrollment has been met, follow-up procedures outlined in Section 12.4 have been conducted on all subjects, and data analysis is concluded. The study may also be terminated early for any reason by the PI-sponsor.

Subjects that are lost to follow-up will be documented in the patient record and in the 21 CFR Part 11 database. In the compliant database, the subject will be marked as “Patient Status Unknown,” along with a corresponding explanation, if any.

12.6 Early Withdrawal of Subject(s)

12.6.1 Criteria for Early Withdrawal

Subjects may voluntarily withdraw from the study at any time. The Principal Investigator may also withdraw a subject from the study at any time based on his/her discretion. Reasons for PI-initiated withdrawal may include, but are not limited to the following:

- Non-compliance of the subject
- Administrative issues
- Disease progression

12.6.2 Follow-up Requirements for Early Withdrawal

Subjects should be seen in clinic or contacted at a minimum of every 3 months for 1 year.

12.6.3 Replacement of Early Withdrawal(s)

Subjects that withdraw from the study prior to receiving PVSRIPO infusion, either voluntarily or due to ineligibility, will be considered non-evaluable; those subjects will be replaced.

12.7 Study Assessments

12.7.1 Medical History

Standard medical history will be obtained and documented per institutional guidelines.

12.7.2 Physical Exam

Standard physical exam and neurological assessment will be conducted and documented per institutional and PRTBTC guidelines.

12.7.3 Radiographic Review

A CT will be obtained to confirm catheter placement prior to beginning the PVSRIPO infusion. A MRI of the brain without gadolinium enhancement will be obtained within 4 hours of

completing the PVSRIPO infusion to monitor distribution of the infusion. A MRI of the brain with gadolinium enhancement will be obtained at all subsequent visits.

Given that imaging following immunotherapy differs greatly from what is typically seen following chemoradiation treatment or treatment with anti-angiogenic compounds, evaluation of response using with Macdonald criteria or RANO criteria is not appropriate in this trial. Immunotherapy can trigger an inflammatory immune response that is observed on imaging. Distinguishing between the inflammatory immune response and progressive disease is difficult. Therefore, an exploratory objective of this study is to describe radiographic imaging post-PVSRIPO treatment. Another exploratory objective of this study is to describe changes in tumor volume based upon radiographic imaging. For that reason, subjects who have gone off study may continue to be followed for collection of MRI measurements. For the purpose of this objective, relative tumor volume is estimated from the MRI using the metric of multiplying the widest tumor diameter with the perpendicular height of the tumor in that same slice.

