9.1.2 Agent Infusion

Refer to the study Investigational Product Handling Plan (IPHP) for additional details regarding the infusate preparation and infusion procedure. The entire volume of the prepared infusate will be provided in a sterile infusion syringe by the investigational pharmacist and connected to the catheter under sterile conditions in the Pediatric Intensive Care Unit (PICU) just prior to beginning of infusion. Due to the complexity of scheduling all of the necessary components for the infusion (operating room time, pharmacy time, and radiology appointments), a +1 day window has been built into the study for the study drug infusion. This means that the infusion is allowed to start the following day after the

biopsy/catheter placement. This will still be considered “day 0” with regard to the protocol and the timing of the subsequent events. At the time of virus injection, emergency drugs, including epinephrine and diphenhydramine will be available and the neurologic status, oxygen saturation, and cardiac rhythm will be monitored. Drug infusion will occur in the PICU so that all other emergency facilities will be available. Patients will be treated with a prophylactic antibiotic prior to biopsy and catheter insertion per DUHS neurosurgical standard practice.

Based on our own experience, previously published reports ⁵ and IRB- and FDA-approved trials using similar infusion techniques, patients will be infused at a rate of 0.5mL/hr. A Medfusion 3500 or 3010a infusion pump will be pre-programmed to a delivery rate of 500 μ L/hr. The infusate will be loaded in a syringe into the syringe pump at the initial onset to avoid any interruptions in the infusion. The total amount of the infusate delivered to the patient will be 3 mL. The infusion pump will be programmed for delivery of the 3.0mL at a rate of 0.5ml/hr, over approximately 6.5 hours. The catheter itself (30 cm length, 1 mm interior diameter) cannot be preloaded with virus suspension. To account for this catheter dead space, the pump will be stopped when the delivered amount is between 3.125 to 3.250 mL. The infusion will be performed using a Medfusion 3500 or 3010a (Smiths Medical ASK, Inc., Minneapolis, MN) syringe infusion pump. The catheter will be removed in the PICU following the post-PVSRIPo infusion MRI. No sedation is required for catheter removal.

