The infusion catheter (PIC 030) and infusion tubing (PIT 400) are manufactured by Sophysa, Inc. (Crown Point, IN). The Infusion Catheter Kit is a 30 cm clear, open-ended catheter (1.0 mm ID/2.0 mm OD) with 1 cm markings for 20 cm. The catheter comes with a 30 cm stainless steel stylet, a barbed female luer lock with cap and a stainless steel trocar. The Infusion Tubing Kit consists of a 3-way stopcock connector with air filter, 4 m of microbore tubing with antisiphon valve, a red, vented cap and a white luer lock cap. The catheter products are packaged sterile and non-pyrogenic and are intended for single (one-time) use only.

Acute Reaction. Any acute reaction symptoms determined to be an acute reaction to the study drug will be managed by the PICU and pediatric neurosurgical teams.

9.1.3 Gadolinium Distribution Quantitation (applies only to patients treated prior to October 31, 2019)

This gadolinium tracking MRI procedure has been removed and applies only to patients treated prior to October 31, 2019. Magnevist® is no longer being manufactured and, as such, is no longer being included in the infusate.

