- **Risk of Infection:** The intracerebral catheter placement and infusion may include the risk of infection. However, similar procedures including stereotactic biopsy and ventriculostomy placement are commonly used in the routine clinical care of patients with malignant brain tumors with a very low and acceptable rate of infection. In the most extreme situation, however, infection may lead to systemic bacterial/fungal sepsis and possibly death. The risk of infection will be minimized though by performing catheter implantations in the Operating Room. Patients will be monitored throughout the course of the study for any signs and symptoms of infection. If an active infection is suspected, patients will be cultured and treated with appropriate antibiotics.
- **Risk of Phlebotomy:** Drawing blood or inserting an intravenous catheter into an arm vein may result in bruising or swelling in the area of the insertion, bleeding at the site of the needle puncture, light headedness, fainting and very rarely, local infection, which may be severe. These risks are reduced by the fact that the blood will be drawn by a qualified physician, nurse or phlebotomist (a professional trained to draw blood).
- **Risks of MRIs:** Risks and/or discomforts associated with MRI scans include anxiety produced from being in a tight, enclosed space (claustrophobia). In addition, the machine operates using a large and powerful magnet, which attracts certain metals. Therefore, people with these metals in their bodies (specifically pacemakers, infusion pumps, metal aneurysm clips, metal prostheses, joints, rods or plates) will be excluded from the study. Patients will also be checked to make sure that they do not bring any metal objects into the MRI facility. Dental fillings are less affected by the magnetic fields generated and are therefore permitted. It will be asked that patients let the physicians conducting this study know of any metal in their bodies other than dental fillings. Depending upon the age of the patient, sedation for imaging may be needed. Risks of sedation include an allergic reaction, aspiration, and over-sedation. Use of an IV may cause bruising. Occasionally, an infection develops at the IV site.

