10.2 Packaging and Labeling

PVSRIPO is formulated in 50 mM sodium phosphate in 0.9% sodium chloride, pH 7.4 with 0.2% human serum albumin. It is provided in sterile, single use containers. PVSRIPO was manufactured at the Biopharmaceutical Development Program/SAIC-Frederick at NCI-Frederick. Prior to October 31, 2019, for tracking intratumoral/intracerebral distribution of the inoculum, the study agent suspension was supplemented with gadolinium-DTPA diamide (Magnevist®) at a final concentration of 1 mM and Magnevist® was stored at room temperature. Magnevist® is no longer being manufactured in the US so has been removed from the infusate along with the corresponding post-infusion MRI within 4h of infusion.

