12 SCREENING AND ON-STUDY TESTS AND PROCEDURES

Table 2. Schedule of Study Tests and Procedures

Description	Within 6 months	Screening: Within 14 days prior to catheter placement	Screening: Within 5 days prior to PVSRIPO	Catheter Placement biopsy, PVSRIPO infusion	After Completion of Infusion	Post infusion (follow-up period) ^a						
Week						0	1	2	4	8	16, 24, 32, 40, 48	
Day		Within 14 days prior to catheter placement	Within 5 days prior to PVSRIPO	0	0	1	7	14	28	56	112, 168, 224, 280, 336	
General Evaluations												
Physical Exam		X	X			X ^b	X	X	X	X		X
Neurologic Exam		X	X			X ^b	X	X	X	X		X
Performance Status		X	X				X	X	X	X		X
Adverse Events ^h	X	X	X			Continuous						
Laboratory Evaluations												
Poliovirus Immunization Booster	X											
CBC w/diff		X				X		X	X	X		X
CMP		X				X		X	X	X		X
PT, aPTT		X										
Serum Pregnancy Test		X	X ^c									
Serum for LSQ and anti-tetanus toxoid IgG	X											
Whole blood for immunologic analysis and/or poliovirus titer (up to 10 mL, except for 4 mL on Day 1 and 6 mL on Day 14)	X	X				X	X	X	X	X	X (at 16 and 24 wks) ^d	
Whole blood for immunologic analysis (not to exceed 3 mL/kg in a 24 hr period or 7 mL/kg in a 8 week period)	X ^e	X ^e					X ^e	X ^e	X ^e	X ^f	X (at 16 and 24 wks) ^{d, f}	
Disease Evaluations												
MRI			X		X ^g (based upon date of enrollment)				X	X		X
CT Scan				X								
Biopsy				X								
Treatment												
PVSRIPO				X								

^a Starting with Day 7 (Week 1), all tests and procedures have a 7-day plus or minus window.

^b Daily after infusion until discharged from hospital

^c Serum pregnancy test, if appropriate, within 48 hours of catheter placement and PVSRIPO

^d At the discretion of the Principal Investigator, an additional blood sample at least 2 years post study drug infusion may be obtained.

^e Whole blood draws for immunologic analysis may be taken (up to 36 mL) at the discretion of the Investigator, but should remain consistent with allowable volumes for pediatric patients depending upon the weight of the child (per Duke policy, the maximum blood volume drawn for research should not exceed 3 mL/kg in a 24 hr period or 7 mL/kg in an 8 week period).

^f At 8, 16, and 24 weeks, up to 76.5 mL of whole blood may be drawn for immunologic analysis (please refer to Duke blood volume policy mentioned above).

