^g Prior to October 31, 2019, MRI to track Magnevist® containing infusate should have been obtained within 4 hours after completion of infusion. This MRI after the infusion was without gadolinium enhancement, but this MRI will not be performed on patients enrolled after October 31, 2019. All other MRIs in the study include gadolinium enhancement.

^h Adverse events directly related to required screening procedures should be recorded.

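### Sections 12.7.3 and 9.1.2 still order a post-infusion MRI that the protocol removed after October 31, 2019, and time catheter removal by it

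*Combined protocol and SAP*

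**What the plan says.** Two current procedural sections assume the post-infusion scan takes place:

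- Section 12.7.3 (Radiographic Review): "A MRI of the brain without gadolinium enhancement will be obtained within 4 hours of" completing the infusion, in order to monitor its distribution. There is no date limit. The section continues: "A MRI of the brain with gadolinium enhancement will be obtained at all subsequent visits".
- Section 9.1.2 (Agent Infusion): "The catheter will be removed in the PICU following the post-PVSRIPo infusion MRI". This too has no date limit.

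Other current sections say the scan has been withdrawn:

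- Section 9.1.3: "This gadolinium tracking MRI procedure has been removed and applies only to patients treated prior to October 31, 2019".
- Section 10.2, on the gadolinium tracer: it "has been removed from the infusate along with the corresponding post-infusion MRI within 4h of infusion".
- Table 2: the post-infusion MRI cell is marked as "based upon date of enrollment", and footnote g says "this MRI will not be performed on patients enrolled after October 31, 2019".
- Section 12.3: the Day 0 list has biopsy, catheter placement, CT and infusion, but no post-infusion MRI.

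On sedation, Section 9.1.3 explains that the earlier patients did not need it for this scan because they were at least 12 years old. Section 11.1 now admits patients from age 4, and Section 9.1.6 says that, depending on age, "sedation for imaging may be needed".

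**The concern.** These are working instructions, not background. Someone who takes imaging from Section 12.7.3 would order a scan whose stated purpose, tracking the infusate, has gone with the tracer. In a young child that scan could require sedation, for which Section 9.1.6 names allergic reaction, aspiration and over-sedation as risks. Someone who takes catheter handling from Section 9.1.2 is told to remove an intracerebral catheter after an event that other sections say will not happen. The catheter point is the more serious one, because no other section of these documents says when removal takes place.

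Scan timing also bears, to a lesser degree, on the exploratory imaging and tumor-volume objectives (Sections 15.6 and 15.7), which are best served by one unambiguous schedule.

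**Working it through.** The plan gives no figure to reproduce. The check is a comparison of sections plus a count of visits.

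**1. The 4-hour scan, for a patient enrolled and treated after October 31, 2019**

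| Section | Is the scan done? |
|---|---|
| 12.7.3 | Yes, no date limit |
| 9.1.2 | Assumed, as the step before catheter removal |
| 9.1.3 | No |
| 10.2 | No |
| 12.3, Day 0 list | Not listed |
| Table 2 and footnote g | No |

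For patients before the cut-off, Section 12.7.3 agreed with the rest. What it lacks is the date limit.

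**2. Catheter removal.** Section 9.1.2 gives a place (the PICU) and an order (after the post-infusion MRI). Section 12.3 covers placement and infusion but not removal. No other timing for removal was found. Once the scan is withdrawn, the sentence refers to something that does not occur.

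**3. Visit count.** Section 12.4 lists ten scheduled post-infusion assessments: Day 1 and Weeks 1, 2, 4, 8, 16, 24, 32, 40 and 48.

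- With MRI: Weeks 4, 8, 16, 24, 32, 40 and 48 = 7.
- Without MRI: 10 − 7 = 3 (Day 1, Week 1, Week 2).

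The columns of Table 2 are broken in the text available, but Section 12.4 is clear and the MRI marks in Table 2 are consistent with it.

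**4. Scans per child beyond the schedule, by reading of Section 12.7.3**

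- The 4-hour scan only, taking the sentence on later visits as describing contrast type: 1.
- Later-visit sentence taken literally, inpatient Day 1 not counted as a visit: 1 + 2 = 3.
- Later-visit sentence taken literally, Day 1 counted: 1 + 3 = 4.

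**5. Other remnants of the same change.** Section 9.1.3 sets the cut-off by date of treatment and footnote g by date of enrollment. A patient enrolled on or before October 31, 2019 but treated after it is classified differently by the two rules. Section 9.1.6, under contrast-agent allergy, still says in the future tense that gadolinium will be infused together with the study drug, which conflicts with Section 10.2.

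**The case against.** The strongest reply is that the intent is plain. The withdrawal appears in the heading and text of Section 9.1.3, in Section 10.2, in the Table 2 cell and in footnote g, and Section 12.3 omits the scan. Against that stand one undated sentence in Section 12.7.3 and one in Section 9.1.2. Staff would probably follow Table 2. This stands as an account of how the conflict arose: it is an editing remnant, not a design decision. It does not settle the catheter sentence, because Table 2 and Section 12.3 say nothing on removal.

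A reader might infer that Section 12.7.3 firmly requires four extra scans per child, and multiply that over the patients still to be treated. The documents do not support this. The sentence on later visits follows one about a scan without contrast, and footnote g draws the same contrast when it says all other MRIs include gadolinium. It may therefore state the type of scan and leave timing to Section 12.4 and Table 2, which agree. Day 1 is an inpatient assessment and a doubtful visit. The number of patients remaining is not given either: Section 5.5 says the first 5 treated patients were reviewed before Amendment 12, not that only 5 had been treated when it took effect.

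A reader might also infer that catheter removal is left wholly undefined. That goes too far. Section 9.1.2 still gives the place and puts removal after infusion, and it refers to the Investigational Product Handling Plan for further detail on the infusion procedure. That plan is not available here and may contain a removal step.

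Nor do the documents support a claim that different centers would produce different imaging data, since the procedures describe conduct at one institution. All sections agree on MRI at Weeks 4 to 48.

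**Conclusion.** The contradiction is real and lies in current operative text. Section 12.7.3 orders a scan that Sections 9.1.3 and 10.2 and Table 2 have withdrawn for patients after October 31, 2019. The only catheter-removal timing in these documents depends on that scan.

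Its size is at least one unscheduled MRI per child if Section 12.7.3 is followed literally, against seven scheduled after infusion. The looser reading of the later-visits sentence could add two or three more, but that reading is not secure. Sedation is a possibility that depends on age; the documents do not say how many patients would need it.

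No sample size, stopping threshold, or primary or secondary endpoint is affected. The point is worth correcting because it concerns procedures in children, not because it alters inference. It rests on two assumptions: that the present text of both sections is meant to govern new patients, and that no instruction outside these documents already resolves the catheter step.

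**What to change.** Reconcile Sections 12.7.3 and 9.1.2 with Sections 9.1.3, 10.2, 12.3 and 12.4 and Table 2. In the same edit:

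- Have Section 12.7.3 refer to a single MRI schedule, and say whether its sentence on later visits concerns timing or contrast type.
- Use one cut-off, by treatment date or by enrollment date, in both Section 9.1.3 and footnote g.
- Bring the gadolinium co-infusion statement in Section 9.1.6 into line with Section 10.2.
- Have the clinical team restate the catheter-removal step in Section 9.1.2 and check it against the Investigational Product Handling Plan.

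Which imaging or removal rule should apply is for the clinical team; none is proposed here. The cost is a wording amendment, with no change to design, sample size or analysis.
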